5.0 Risk Management Procedures

Data Safety Monitoring Plan (DSMP)

The local Data Safety Monitoring Plan for this trial will include the following requirements:

1. This study will identify, monitor, and report adverse events (AE) and unanticipated problems (UP).
2. Expedited reporting to the IRB is required for unanticipated problems (UP) or unexpected serious adverse events (SAE) that may be related to the study protocol as follows:

Any event or problem that is unexpected AND possibly, probably, or definitely related to study participation AND one of the following:

- Is fatal, life-threatening, or serious (SAE + UP) REPORT within 7 calendar days
- Suggests greater risk of harm to study participant(s) than..... REPORT within 30 calendar days
was previously known or recognized

3. Expedited SAE/UP reporting to the IRB should include study and grant number, PI, description of the event or problem, why it merits expedited reporting, dates the event was reported to IRB, FDA and other governing bodies, and any corrective action planned or taken in response to the event or problem, e.g. study suspension, consent or protocol changes, additional training or security measures.
4. Reporting is required by the investigator to and following the guidance of any other applicable oversight bodies, but not limited to IRB, local DSMB and FDA. All communication from these oversight bodies regarding any applicable SAE/UP must be reported to IRB according to the Data and Safety Monitoring Policy.

The PI, [name], the Co-Investigators, and the HCWP nurse coordinator(s) will be responsible for ongoing monitoring of all recruitment, data collection and subject confidentiality procedures at this site. They will meet at least bi-weekly to review all aspects of the study. Subjects will be closely monitored by the PI, research and clinical staff to ensure subject safety and to ensure that procedures are in place to maintain privacy and confidentiality, progress of study, integrity of the data, procedure reviews and for discussion of pertinent scientific literature or events which could affect the benefit to risk ratio. All serious and unexpected adverse events and/or major breaches of confidentiality will be reported to the IRB according to regulations outlined in the IRB *Reference Manual for the Use of Human Subjects*. All AE's, SAE's generated from the Hemophilia Center of Western PA will be sent following CRF and eCRF reporting guidelines to IRB. A report summarizing the above local DSMP activities will be submitted to the IRB at the time of annual renewal.

Data will be reviewed on an ongoing basis by the local Data Safety Monitoring Committee (DSMC). A Data Safety Monitoring Committee (DSMC) will review all data collected on the study. All DSMC members will have voting rights. The DSMC will review data for all subjects enrolled in the study protocol and determine if the risk benefit ratio is sufficiently favorable that it is appropriate to continue the trial.

The events are:

- A subject develops anaphylaxis in association with administration of rVWF and/or TA
- A subject develops a thrombotic event in association with the administration prophylaxis with the exception of intravenous (IV) infusion site thrombophlebitis.
- A subject develops severe or severe bleeding requiring prolonged and/or intense treatment exceeding study-related dosing.
- A subject develops a Grade 2 or greater allergic reaction in association with rVWF and/or TA defined as follows using the CTCAE grading.⁴⁰
 - Grade 2 Transient flushing, rash, or drug fever $\geq 38^{\circ}$ C.
 - Grade 3 Symptomatic bronchospasm; with or without urticaria; parenteral medication(s) indicated; allergy-related edema/angioedema; hypotension
 - Grade 4 Anaphylaxis

In addition to halting enrollment and further treatment, such an event will be handled as a serious adverse event (SAE) and reported in an expedited time frame to the FDA. The data concerning the event and subject with input from the site HTC Co-Investigator will be reviewed by the DSMC along with all other available data to determine appropriate follow-up, with a decision to continue enrollment and treatment of subjects at that time. If the decision is made to discontinue the study, the Co-Investigators will be notified and the appropriate final study evaluations (Final Visit) will be performed on all subjects enrolled in the study at that time.

Additionally, the following may also stop further subject enrollment and treatment.

- The DSMC warrants temporary suspension of enrollment for further review of data generated to date.
- The PI determines that a medically important event warrants further evaluation by the DSMC. In these cases the required follow-up as determined by the PI and/or DSMC will be performed. The DSMC will determine if it is appropriate to reinitiate enrollment in the study. The IRB will be informed of such decisions.

Local Adverse Event Reporting

All adverse events experienced by study subjects from the time of dosing until 30 days after administration is to be recorded on the CRF, regardless of the severity of the event or its relationship to study treatment.

The serious AE reporting procedures are based on the “Cancer Therapy Evaluation Program: Common Terminology Criteria for Adverse Events” (CTCAE) v 4.03, June 14, 2010.⁴⁰ Subjects will report to HTC co-investigator or to the HTC nursing coordinator, any AE or SAE. AE's will be classified as mild (does not interfere with routine activities), moderate (interferes somewhat with routine activities), or severe (impossible to perform routine activities). The following algorithm will be used to assess the causality of all AE's:

- Not related: The event can readily be explained by factors not involving rVWF and/or TA, and a temporal relationship with rVWF and/or TA, does not exist.
- Possibly related: A clinical event, including laboratory test abnormality, with a reasonable time sequence to administration of rVWF and/or TA, but which could also be explained by concurrent disease or other drugs or chemicals. Information on drug withdrawal may be lacking or unclear.
- Probably related: The temporal relationship between the administration rVWF and/or TA is compelling, and the event cannot be explained by the subject's medical condition or other therapies.
- Related: The event follows a reasonable temporal sequence from administration of rVWF and/or TA follows a known or suspected response pattern to rVWF and/or TA, is confirmed by improvement upon stopping the agent (de-challenge) and reappears upon repeated exposure to rVWF and/or TA.

All AEs, regardless of severity, will be followed up by HTC Investigator until satisfactory resolution. All subjects experiencing AEs will be monitored until symptoms subside and any abnormal laboratory values have returned to baseline, or until there is a satisfactory explanation for the changes observed, or until death, in which case a full pathologist's report will be supplied, if possible. Withdrawal from the clinical study and therapeutic measures shall be at the discretion of the investigator.

As required by the University of Pittsburgh Institutional Review Board, if there is an unexpected, serious internal adverse event (life threatening or fatal) that is determined to be associated with rVWF and/or TA, it will be reported to the IRB within 24 hours. If the event is not serious, unexpected or related to either agent, it will be reported within 5 days. External adverse events that are unexpected, related to either agent and determined to place the subject at greater risk than previously recognized, will be reported within 10 working days of notification.

Adverse Event (AE) Reporting at sites:

All events must be assessed to determine the following:

- If the event meets the criteria for an SAE
- The relationship of the event to study treatment
- The severity of the event

An AE is any untoward medical occurrence in a subject in whom a pharmaceutical product is administered and that does not necessarily have a causal relationship with this treatment. An AE can therefore be any unfavorable and unintended sign (including an abnormal laboratory finding), symptom, or disease temporally associated with the use of a pharmaceutical product, whether or not related to the pharmaceutical product.

A serious adverse event (SAE) is any untoward medical occurrence that at any dose:

- results in death
- in the view of the Investigator, places the subject at immediate risk of death (a life-threatening event), but does not include an event that, had it occurred in a more severe form, might have caused death
- requires inpatient hospitalization or prolongation of existing hospitalization
- results in persistent or significant disability/incapacity, or
- results in a congenital anomaly/birth defect.

An SAE may also be any other medically important event that, in the opinion of the Investigator, may jeopardize the subject or may require intervention to prevent one of the other outcomes listed in the definition above. (Examples of such medical events include allergic bronchospasm requiring intensive treatment in an emergency room or convulsions occurring at home that do not require an inpatient hospitalization.)

In this study, the following events are considered medically important and must be reported as SAEs:

- A subject develops other bleeding in association with administration of rVWF and/or TA.
- A subject develops anaphylaxis in association with administration of rVWF and/or TA.
- A subject develops a thrombotic event in association with the administration of rVWF and/or TA, with the exception of intravenous (IV) infusion site thrombophlebitis.
- A subject develops a Grade 2 or greater allergic reaction in association with administration of rVWF and/or TA defined as follows using the CTCAE Evaluation.
 - Grade 2 Transient flushing, rash, or drug fever $\geq 38^{\circ}\text{C}$.

- Grade 3 Symptomatic bronchospasm; with or without urticaria; parenteral medication(s) indicated; allergy-related edema/angioedema; hypotension
- Grade 4 Anaphylaxis

Any SAE experienced by the subject from the time of dosing until 30 days after rVWF and/or TA administration is to be recorded on an SAE Form, regardless of the severity of the event or its relationship to study treatment. SAEs must be reported to the PI. Any SAE ongoing when the subject completes the study or discontinues from the study will be followed by the Investigator until the event has resolved, stabilized, or returned to baseline status.

A serious pre-treatment event associated with the conduct of the study experienced by the subject after signing the ICF, but before administration of study treatment is to be recorded on the Serious Adverse Reaction (SAE) CRF and faxed (and electronically uploaded) to the PI within 24 hours of the study site staff becoming aware of the event.

In order to adhere to all applicable laws and regulations for reporting an SAE, the study site will formally notify the PI within 24 hours of the study site staff becoming aware of the SAE. It is the Investigator's responsibility to ensure that the SAE reporting information and procedures are followed. A death must be recorded on the appropriate CRF and electronic CRF (eCRF). All causes of death will be reported as SAEs.

Reporting Information for SAEs

Any SAE that occurs after any subject receives rVWF and/or TA and any serious pre-treatment events must be reported to the PI within 24 hours of the study site staff becoming aware of the event. This report must be submitted regardless of whether or not the subject has undergone any study-related procedures or received study treatment and *regardless of severity or relationship to study treatment*. To report initial or follow-up SAE information and serious pre-treatment medical event information, enter the information in the CRF and web-based CRF. If the database is not available, fax a completed SAE form to the following or, if fax is not possible, call the number below to report the information. *Emergency Contact Numbers:* [contact]; [contact] (daytime); [contact] (evening and weekends)

Safety Classifications and Relationship of Events to Study Treatment

The following definitions should be considered when evaluating the relationship of AEs and SAEs to the study treatment:

Relationship of Event to Study Treatment

Unrelated	Any event that does not follow a reasonable temporal sequence from administration of study treatment AND that is likely to have been produced independently by the subject's clinical state or other modes of therapy administered to the subject.
Unlikely	Any event that does not follow a reasonable temporal sequence from administration of study treatment OR that is likely to have been produced by the subject's clinical state or other modes of therapy administered to the subject.
Possibly	Any reaction that follows a reasonable temporal sequence from administration of study treatment OR that follows a known response pattern

	to the suspected drug AND that could not be reasonably explained by the known characteristics of the subject's clinical state or other modes of therapy administered to the subject.
Related	Any reaction that follows a reasonable temporal sequence from administration of study treatment AND that follows a known response pattern to the suspected drug AND that recurs with re-challenge, AND/OR is improved by stopping the drug or reducing the dose.

Severity of Events

The following definitions should be considered when evaluating the severity of AEs and SAEs:

Mild	Symptom(s) barely noticeable to subject or does not make subject uncomfortable; does not influence performance or functioning; prescription drug not ordinarily needed for relief of symptom(s) but may be given because of personality of subject.
Moderate	Symptom(s) of a sufficient severity to make subject uncomfortable; performance of daily activity is influenced; subject is able to continue in study; treatment for symptom(s) may be needed.
Severe	Symptom(s) cause severe discomfort; symptoms cause incapacitation or significant impact on subject's daily life; severity may cause cessation of treatment with study treatment; treatment for symptom(s) may be given and/or subject hospitalized.

A prescheduled or elective procedure or a routinely scheduled treatment will not be allowed during the study period.

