This is a prospective, randomized single-center phase III pilot clinical trial comparing recombinant von Willebrand factor (rVWF, Vonvendi®) plus tranexamic acid (TA, Cyclokapron®) vs. rVWF alone to reduce postpartum hemorrhage (PPH) in women with von Willebrand disease (VWD). We *hypothesize* that intravenous rVWF given just before delivery plus intravenous tranexamic acid within 3 hours of delivery is superior to rVWF alone in reducing postpartum blood loss.

Objective:

The **Primary Objective** is to determine the efficacy of rVWF plus TA vs. rVWF alone in reducing postpartum hemorrhage in women with VWD.

The **Secondary Objectives** are to evaluate safety, tolerability, and mechanism of rVWF plus TA vs. rVWF alone in reducing PPH in women with VWD.

Endpoints:

The **Primary Endpoint** is quantitative blood loss (QBL) calculated by a labor suite nurse at delivery. The **Secondary Endpoints** include safety assessment by lochial blood loss by pictorial blood assessment chart (PBAC), blood products, transfusion, and hysterectomy within 21 days of delivery; and mechanism of PPH reduction by VWF assays, fibrinogen, and d-dimer.

Study Population:

Study subjects will be females age \geq 18 years of age with von Willebrand disease, defined by VWF:RCo <0.50 IU/dL (historic) and previous bleeding history, undergoing vaginal or caesarean section delivery. A total of 20 eligible subjects with VWD will be enrolled in this 2-year trial.

Site Enrolling Subjects:

Pilot: Participating site is HCWP, and Magee Hospital obstetricians.

Description of Study Intervention:

There are two study interventions: rVWF plus tranexamic acid vs. rVWF alone. Recombinant von Willebrand factor (rVWF, Vonvendi®) is an FDA-approved clotting factor approved for treatment or prevention of bleeds including postpartum hemorrhage hemorrhage in VWD. It is an intravenous agent administered in single-use vials containing approximately 650-1300 IU per vial as a sterile, lyophilized powder. The vials are reconstituted with 5-10 ml vial of sterile water for injection, USP, which is transferred by two-way needle into the lyophilized powder for reconstitution, and the reconstituted vial infused over 5-10 minutes, at 80 IU/kg (per pre-pregnancy weight) at delivery (or epidural), and days 1 and 2 postpartum.

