2.0 Background and Significance

2.1 Significance

Von Willebrand disease (VWD) is the most common congenital bleeding disorder, occurring in 1% of the population.¹ It is caused by quantitative or qualitative deficiency of von Willebrand factor (VWF). VWF is a multimeric plasma glycoprotein which serves both as a carrier molecule for factor VIII and as an adherent protein that mediates platelet adhesion to damaged vascular endothelium.^{2,3} The bleeding in VWD is primarily mucosal, including bruising, epistaxis, menorrhagia, and postoperative bleeding, and, in women of child-bearing years, reproductive tract bleeding, including postpartum hemorrhage (PPH).^{3,4} Women with VWD have a 1.5-fold greater odds of PPH than controls,⁵ with an incidence of 5.5%.⁶ Over one-quarter of women with VWD and PPH are anemic, or twice as many as non-VWD women with PPH, and are more likely to require a red blood cell transfusion.⁶ When severe, < 7 g/dL, anemia is refractory to routine iron supplementation and associated with a 2-fold greater odds for maternal death.⁷ These data suggest PPH is a significant cause of maternal morbidity and mortality.

Postpartum hemorrhage is the leading cause of maternal death in the world and accounts for one third of maternal deaths in the United States. Defined as blood loss exceeding 1000 mL in first 24 hours with vaginal delivery or cesarean delivery,⁸ PPH peaks in the first 2-3 hours postpartum, a time during which there is early activation of the fibrinolytic system, with a 2-fold increase in TPA (tissue plasminogen activator).⁹ Overall, while uterine atony is the major cause of PPH, accounting for 63% of PPH cases,¹⁰ and uterotonic agents are effective in reducing PPH,¹⁰ but in 37% they may fail.

Current guidelines indicate that management of postpartum hemorrhage should include hemostatic agents, including antifibrinolytic agents, e.g. tranexamic acid, which is an inhibitor of plasmin-mediated

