The goal of the current study will be to obtain preliminary information on the safety and efficacy of rVWF given at 80 IU/kg at delivery and day 1, day 2, with or without TA 1 gm IV within 3 hours of delivery in reducing postpartum hemorrhage in 20 pregnant VWD subjects. If the study recruitment, randomization, drug administration, data collection and management are feasible, then the large, multicenter phase III trial will be initiated. As both drugs are FDA-approved and have been previously used in VWD patients without adverse effects, we anticipate none during the study. If any subject experiences any grade 3 or higher treatment-related toxicity, blood loss, allergic reaction (fever, chills, hives, tachycardia, chest discomfort), or thrombosis, the decision to continue the study will be made by a local Data Safety Monitoring Committee.

DOSING SCHEMA

Study Arms	No. Subjects	Study Drug(s) at Delivery	Study Drug Postpartum
Arm A	10	rVWF 80 IU/kg + TA 1 gm	rVWF 80 IU/kg days 1 and 2
Arm B	10	rVWF 80 IU/kg	rVWF 80 IU/kg days 1 and 2

rVWF is a single-dose IV infusion given over 5-10 minutes. TA is a single-dose IV infusion given over 10 minutes.

Screening Procedures. Following informed consent, subjects will be screened at the Hemophilia Center of Western PA, by medical history, physical examination, vital signs (height, weight, blood pressure, respirations, heart rate, temperature), and baseline laboratory studies within 3 weeks of the escalating dose study. Baseline labs will include **VWF assays** (VWF:RCo, VWF:Ag, FVIII:C); **coagulation tests** (fibrinogen, d-dimer), **blood counts** (hemoglobin, hematocrit, platelet count); and **iron tests** (Fe, TIBC, ferritin). All tests will be drawn at screening (32-39 weeks' gestation), and all tests except for the iron tests will be drawn on admission for childbirth, at day 1, day 2, and day 21 postpartum. Blood draws will be performed on day 0 pre-delivery by the Magee Labor and Delivery unit as soon as the IV is started. Subsequent blood draws on day 1 and day 2 will be coordinated through HCWP research team. The total blood draw is 49 cc (~2.5 tbsp), including 13 cc (~1 tbsp) at screening; and 9cc (~0.6 tbsp) at the remaining 4 blood draw draws. See Appendix 1.

Up to 30 subjects will be screened to assure 20 subjects are enrolled. Subjects will be randomized to rVWF + TA vs. rVWF alone at delivery. Subjects will receive only the study drug(s) to which they are

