Laboratory Assays. One blue top (5.0 cc) will be obtained for VWF assays: VWF ristocetin cofactor by platelet aggregometry, VWF antigen by ELISA, FVIII activity by chromogenic assay on an ST4 analyzer; and coagulation assays: fibrinogen by Clauss method, and d-dimer by quantitative assay run in the ITxM/Vitalant Coagulation Laboratory, Pittsburgh. One purple top (4.0 cc) will be drawn for blood counts (hemoglobin, hematocrit and platelets), and one SST tube (4.0 cc) will be drawn for iron studies (iron, TIBC, and ferritin) to be run by standard methods at UPMC University Clinical Laboratories.

Study Termination. A subject will be terminated from the study if any of the following situations arise: the subject develops grade 3 or higher toxicity, allergic reaction, or thrombosis at any time during study.

Study Visit 1: Screening, 32-39 Weeks' Gestation

This visit will take place prior to infusion of study drug(s) in order to confirm eligibility requirements. The following tests or assessment will be performed at the Screening Visit.

- The PI, [name] or a co-investigator will discuss the study with potential study subjects, answer questions and assure there is adequate time for the potential subject to decide to participate in the study. The potential subject may sign consent or take the consent with them to discuss with family members or other members of the healthcare team. If the potential subject is interested in participating in the study, she may sign the consent document.
- Medical history will include age, all medical diagnoses, current medications, any allergies.
- Vital signs will include blood pressure, temperature, respirations, pulse, weight and height
- Blood draw: a 13 ml (1 tbsp) plasma sample for blood counts and iron studies by UPMC University Clinical Laboratories; and VWF assays and coagulation tests by the ITxM/Vitalant Coagulation Laboratory, Pittsburgh.
- The subject will be randomized and informed of the group to which she is randomized.

Study Visit 2: Admission for Childbirth

This visit begins on admission for childbirth.

- Interim medical history, new diagnoses, medications, allergies.
- Blood draw: a 9 ml plasma sample for blood counts at UPMC University Clinical Laboratories, and VWF assays and coagulation tests by the ITxM/Vitalant Coagulation Laboratory, Pittsburgh.

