Blood Sample Storage. Blood samples will be stored indefinitely at the Hemophilia Center of Western PA under the control of [name]. Samples will be labeled with code numbers, and information linking the code numbers to the subjects' identities will be kept in a separate, locked file at the Hemophilia Center.

Adverse events. The analysis of adverse events, including allergic reaction, thrombosis, and other bleeding, will be based on the number of subjects with adverse events, and incidence rates will be calculated as the number of subjects with an event divided by the number of subjects exposed to drug. Subjects with multiple events will be counted only once in the numerator. For analysis, the highest-grade severity will be considered, and for analysis of duration, the multiple episodes will be summed. Adverse events will be summarized, and each event reported by a subject will be counted repeatedly. The corresponding incidence rates for adverse event episodes will be calculated by the number of adverse event cases over the number of doses. Adverse event incidence rates will be categorized by body system, relationship to study drug, severity of adverse event, age, sex, time of onset of adverse event, and duration of adverse event. Laboratory variables will be analyzed by descriptive statistics.

Sample Size and Power for Pilot Study

Pilot studies require a minimum of nine subjects to prevent an unnecessarily high number of subjects to receive a study drug, but a high enough number to provide insight into safety and efficacy parameters for a study drug.⁴¹ The minimum planned sample size of 20 evaluable subjects also provides adequate power to

evaluate the success and feasibility of the study.⁴¹ The study is considered successful if treatment of fewer than or equal to 6 of the 20 subjects is assessed ineffective or unsafe. The study is considered feasible if procedures, i.e. recruitment, randomization, and study drug administration can be performed successfully.

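### The two places that set a trial-level safety trigger disagree on event, grade and consequence, and the bleeding trigger is undefined and differs by arm

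*Combined protocol and SAP*

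**What the plan says.** Two places say what happens to the trial after a safety event.

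- **Section 3.2, paragraph before the Dosing Schema.** The trigger reads "If any subject experiences any grade 3 or higher treatment-related toxicity, blood loss, allergic reaction", followed by symptom examples in brackets and then thrombosis. The consequence is that a local DSMC decides whether the study continues. No pause is stated.
- **Section 5.0, Data Safety Monitoring Plan.** Four events are listed: anaphylaxis linked to study drug; a thrombotic event linked to treatment, other than infusion-site thrombophlebitis; "severe bleeding requiring prolonged and/or intense treatment exceeding study-related dosing"; and "A subject develops a Grade 2 or greater allergic reaction in association with rVWF and/or TA". The next paragraph gives the consequence: "In addition to halting enrollment and further treatment, such an event will be handled as a serious adverse event". DSMC review and a decision on resuming come afterwards.

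Other rules lie close by but do different jobs. Study Termination in Section 3.2 ends one woman's participation for "grade 3 or higher toxicity, allergic reaction, or thrombosis at any time during study" and has no bleeding item. The list of medically important events in Section 5.0 governs SAE reporting, and its bleeding item has no severity threshold.

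Two treatment provisions bear on the bleeding trigger. Section 3.2 gives Arm A a second TA dose if bleeding continues 30 minutes after the first and has no counterpart for Arm B. Section 4.6 says that a bleeding episode in any subject is treated with rVWF or another hemostatic agent.

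**The concern.** A trial-level safety rule has to give the same answer wherever it is read. Here the same reaction can pause the trial under one section and go unmentioned, or go to the DSMC without a pause, under the other.

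The practical stake is the women already in the trial. They are randomized at 32 to 39 weeks, dosed at delivery and again on days 1 and 2, and delivery cannot wait for a committee. Section 5.0 sets no deadline for the review. It does not say what happens during a halt to a woman who is randomized but undelivered, or who is between doses. With 10 women per arm, each one who misses assigned treatment is 1/10 of her arm.

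Bleeding is also what the trial measures, so a loosely worded bleeding trigger sits next to the primary endpoint in an open-label comparison.

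**Working it through.** **Step 1: the two triggers side by side.** The grade qualifier in Section 3.2 can govern the whole list (reading A) or toxicity alone (reading B).

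| Event | Section 5.0 | Section 3.2, reading A | Section 3.2, reading B |
|---|---|---|---|
| Grade 2 allergic reaction, e.g. rash | Halt, then DSMC | Not listed | DSMC decides, no halt stated |
| Grade 1 allergic reaction | Not listed | Not listed | DSMC decides |
| Blood loss that is not severe | Not listed | Not listed | DSMC decides |
| Severe bleeding treated beyond study dosing | Halt, then DSMC | DSMC decides, if grade 3+ and treatment-related | DSMC decides |
| Infusion-site thrombophlebitis | Excepted | Only if grade 3+ | No exception stated |

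Neither reading makes the columns agree. Reading A is narrower than Section 5.0 on allergy; reading B is broader on allergy and on blood loss. The symptom examples in Section 3.2 include fever and hives, which lie close to the rash and drug fever that Section 5.0 calls Grade 2, so reading B cannot be dismissed. The Study Termination rule has the same ambiguity.

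**Step 2: the bleeding trigger.** It gives no volume, no grade and no list of qualifying treatments. The other three Section 5.0 events require an association with study treatment; this one does not. An Arm A woman who receives a second TA dose is still within study dosing. An Arm B woman given any TA has exceeded it. The words about prolonged or intense treatment must also be met, but they are undefined.

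**Step 3: how often might it fire?** The plan states no halting probability and no rate for this event, so there is no figure to reproduce. Inputs:

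- N = 20 (synopsis; 10 + 10 in the Dosing Schema).
- PPH rate p = 5.5%, or up to one-third despite factor replacement (both Section 2.1). PPH is defined there by volume alone, above 1000 mL in 24 hours.
- f, the share of PPH that meets the trigger: not in the documents, assumed 10% to 100%.

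With independent women, P(at least one) = 1 − (1 − p·f)^20.

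| f | p = 5.5% | p = one-third |
|---|---|---|
| 10% | 1 − 0.9945^20 = 10% | 1 − 0.9667^20 = 49% |
| 25% | 24% | 82% |
| 50% | 43% | 97% |
| 100% | 1 − 0.945^20 = 68% | 1 − 0.6667^20 = 99.97% |

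An even chance of a halt needs a per-woman rate of 1 − 0.5^(1/20) = 3.4%. That is 0.034/0.055 = 62% of PPH at the lower rate, or 0.034/0.333 = 10% at the upper.

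**The case against.** Section 5.0 is the dedicated monitoring section, and it is explicit once one of its four events is recognized. Its halt is a pause followed by a decision on resuming, which is compatible with Section 3.2 leaving continuation to the DSMC; Section 3.2 may simply be silent on the pause. Comparisons between arms are descriptive, so no formal inference depends on the rule. Few women would be caught: with even accrual over 2 years and about 4 weeks from screening to delivery (Schedule of Events), 20 × 4/104 is about 0.8 women awaiting delivery at any time. All of this is fair, and it limits the uncertainty to lower-grade allergic reactions, blood loss, and whether a halt comes before the DSMC decides. It does not make the two lists agree.

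Several stronger readings are tempting and do not stand:

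- That three places define when the trial stops. Study Termination concerns one subject, and the other nearby list concerns reporting.
- That a Grade 2 rash might have no consequence at all. Section 4.6 stops the drug concerned if signs of allergy appear during administration, and Section 5.0 makes the reaction a reportable SAE.
- That the success rule in Section 3.3, "fewer than or equal to 6 of the 20 subjects is assessed ineffective or unsafe", contradicts a halt at the first event. It is an end-of-study criterion, and a trial can pause, resume, finish and then be judged against it.
- That a halt loses endpoint data. Blood loss at delivery is calculated by the labor suite nurse and taken from the chart whether or not study drug is given. What is at risk is the assigned treatment.

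**Conclusion.** The conflict between Section 3.2 and Section 5.0 is in the text and holds on either reading of the grade qualifier. It changes what the trial does after a Grade 2 allergic reaction or a bleed, in a study that the protocol itself rates as greater than minimal risk. The bleeding trigger cannot be applied consistently as worded, and its reference to study dosing sets a different bar in each arm.

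The size of the bleeding problem is uncertain. A reader might infer from the PPH rates that a halt is likely, but those rates describe blood loss above 1000 mL, and the trigger is narrower. The 10% to 99.97% range rests on the assumed qualifying share, on independence between women, and, at its upper end, on a one-third rate that the protocol gives only as a maximum. It supports saying that a halt is a material possibility that the plan has not quantified, and no more.

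**What to change.** Reconcile Section 3.2 and Section 5.0 into one trial-level table giving, for each event, the grade, the relatedness required, the consequence (referral to the DSMC, pause of enrollment, pause of treatment) and who decides. Keep it separate from the subject-level Study Termination rule and the SAE reporting list, and have each point to the other. In addition:

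- state in both parts of Section 3.2 whether grade 3 or higher governs the whole list or toxicity only;
- define the bleeding event in measurable terms that apply identically in both arms, and say whether relatedness is required;
- state what happens during a halt to women who are randomized but undelivered or between doses, and how quickly the DSMC must review;
- once the event is defined, report the chance of at least one halt in 20 women at the rates assumed.

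Which thresholds and consequences are intended is for the sponsor and DSMC to decide. The cost is protocol wording agreed with the DSMC; no extra subjects, visits or data are needed.
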